Table 5: Optional PK/PD Sampling for Intensive PK/PD for Subset of Patients in Cohort 1 and 2

Study Day ^a	Day 2 (24 hours post Day 1 dose (± 4 hours))	Day 4 (72 hours post Day 1 dose, ± 24 hours)	Day 86 (24 hours post Day 85 dose (± 4 hours))	Day 88 (72 hours post Day 85 dose, ± 24 hours)	Day 92 (168 hours post Day 85 dose, ± 24 hours)
PK samples	X	X	X	X	X
Blood sample for PD panel ^b	X	X	X	X	X

^a A subset of Cohort 1 and 2 patients may undergo a more intensive PK/PD sampling specified in this table. All other assessments are to be performed per [Table 3](#), [Table 4](#), and [Table 6](#).

^b PD samples will be collected to assess serum total and free properdin and CAP activity.

Abbreviations: CAP = complement alternative pathway; PD = pharmacodynamic(s); PK = pharmacokinetic(s).

Table 6: Schedule of Activities – Day 99 Through End of Follow-up Period, Cohorts 1 and 2

Study Day	Day 99	Day 127 ^a	Day 155	Day 183 ^a	Day 211 /ET/ Unscheduled	Complement Activity Follow-up ^b
Window (Day)	± 3	± 3	± 3	± 3	± 3	±14
Physical examination					X	
Abbreviated physical examination	X		X			
Vital sign measurements	X		X		X	
Triplicate ECG	X		X		X	
Hematology ^c	X		X		X	
Clinical chemistry ^c	X		X		X	
Coagulation ^c	X		X		X	
Urinalysis (including spot urine)	X		X		X	
Serum/urine pregnancy test	X		X		X	
PK samples	X		X		X	
Blood samples for PD panel (serum total and free properdin, CAP activity)	X		X		X	X
Biomarkers ^d	X		X		X	
Immunogenicity (ALXN1820 ADA) ^e			X		X	
Assessment of VOC ^f	←Monitor continuously→					
Review patient diary ^g	X	X	X	X	X	X
Review safety card ^h	X	X	X	X	X	X
Concomitant medications	←Monitor continuously→					
Adverse events ⁱ	←Monitor continuously→					

^a Visit may be performed remotely (phone or video calls).

^b If CAP activity has not returned to a normal range or 80% of the baseline level at the end of the Follow-up Period, patients may have additional Follow-up Visits every 12 weeks until CAP activity has been confirmed to either have returned to a normal range or 80% of the baseline level. This visit may be completed at home.

Table 6: Schedule of Activities – Day 99 Through End of Follow-up Period, Cohorts 1 and 2

^c Non-fasting blood samples will be obtained.

^d Collection of blood (for serum, citrated and K2-EDTA, or P100 plasma) and urine.

^e In case of any suspected case of hypersensitivity or anaphylaxis additional samples for the assessment of ADA may be collected at or near the time of the event.

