6. SUPPORTING DOCUMENTATION

6.1. Technical Specifications for Derived Variables

Adverse Events

The analysis of AE is described in detail in Section **Error! Reference source not found.**

TEAEs are events with start dates and start times on or after the date and time of the first dose of study intervention and up to 100 days after the last dose of the study intervention. If the start date of an AE is partially or completely missing and the end (stop) date and time of the AE do not indicate that it occurred prior to the first dose, then the determination of treatment-emergent status will be based on the following:

- If the start year is after the year of the first study intervention dose, then the AE is treatment emergent; else,
- If the start year is the same as the year of the first study intervention dose and
 - the start month is missing, then the AE is treatment emergent; else if
 - the start month is present and is the same or after the month of the first study intervention dose, then the AE is treatment emergent; else,
- If the start date is completely missing, then the AE is treatment emergent.

All other AEs are considered pretreatment AEs.

If the relationship to study intervention is missing for TEAEs, then the relationship will be counted as related to study intervention for the listing tables. Missing severity for TEAEs will be counted as Grade 3.

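### SAP 6.1 tests partial AE start dates only against the first dose, so an AE whose known month or year lies wholly after the 100-day window is flagged treatment-emergent, while the same AE with a full date is classed as pretreatment (minor)

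*SAP*

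**What the plan says.** SAP 6.1 (Adverse Events) gives two rules.

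- **Complete dates.** The window has both ends. It opens when dosing begins, and its upper limit is "up to 100 days after the last dose of the study intervention".
- **Partial or missing start dates.** One check comes first, on the stop date: the rule applies if "the end (stop) date and time of the AE do not indicate that it occurred prior to the first dose". The known parts of the start date are then compared with the first dose. By year: "If the start year is after the year of the first study intervention dose, then the AE is treatment emergent; else". Within the same year, a missing month gives treatment-emergent; otherwise the test is whether "the start month is present and is the same or after the month of the first study intervention dose". A completely missing start date is treatment-emergent.

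The rule closes with "All other AEs are considered pretreatment AEs". For AEs that are treatment-emergent, a missing relationship is then counted as related and a missing severity as Grade 3.

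AE collection outlasts the window. Protocol 8.3.1 collects AEs from consent to the last follow-up visit. Protocol 1.1 and SAP 4.1 put follow-up at 18 weeks (126 days), or longer if complement activity has not recovered. Under Protocol 1.3, Table 6, footnote b, "patients may have additional Follow-up Visits every 12 weeks until CAP activity has been confirmed". SAP 4.2.1 shows the treatment-emergent flag in the AE listing.

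**The concern.** A partial date is often ambiguous, and calling an ambiguous AE treatment-emergent is an ordinary cautious convention. The problem is the partial date that is not ambiguous. If the recorded month or year begins after the window has closed, the AE cannot have started inside it, yet the rule still flags it. The rule uses decisive information at the lower end (a stop date, month or year before the first dose) and ignores it at the upper end.

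Two identical late events can then carry opposite labels, depending only on whether the site recorded the day. One is treatment-emergent. The other is called pretreatment although it began months after dosing started. The first also attracts the related and Grade 3 defaults if those fields are blank. Safety is the primary endpoint and the flag is part of its derivation, so the rule should not turn on how complete a date is.

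**Working it through.** **Inputs**

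- Last planned dose: Day 85 in Cohorts 1 and 2 (Protocol 1.3, Tables 3 and 4).
- Follow-up: 126 days (Protocol 1.1; SAP 4.1).
- Window end for complete dates: last dose + 100 days (SAP 6.1).
- Complement extension: one further visit after 12 weeks = 84 days (Protocol 1.3, Table 6, footnote b).
- Assumed, because the documents give no dosing dates: first-dose dates running through all 365 days of 2023.

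**Step 1: the plan's own figure.** 85 + 126 = 211, which reproduces Day 211.

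**Step 2: time outside the window.** Window end = 85 + 100 = Day 185. Gap = 211 − 185 = 26 days. With the +3-day visit window it is 29 days; with one 12-week extension (to Day 295) it is 26 + 84 = 110 days. After early discontinuation, Administrative Change Letter #3 carries over the same follow-up schedule, counted from the last dose, so the gap is again 126 − 100 = 26 days.

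**Step 3: worked cases within planned follow-up**

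| First dose | Last dose | Window end | Day 211 | Post-window days in a month wholly after the window |
|---|---|---|---|---|
| 15 Feb 2023 | 10 May 2023 | 18 Aug 2023 | 13 Sep 2023 | 13 of 26 (1–13 Sep) |
| 15 Jun 2023 | 7 Sep 2023 | 16 Dec 2023 | 11 Jan 2024 | 11 of 26 (1–11 Jan) |
| 2 Oct 2023 | 25 Dec 2023 | 3 Apr 2024 | 29 Apr 2024 | 0 of 26 (all in April) |

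- Row 1: an AE dated September 2023, day unknown, is treatment-emergent (same year, month after February). The same AE dated 5 September 2023 is after 18 August, so it is not, and becomes pretreatment.
- Row 2: January 2024 or just 2024 is treatment-emergent (year after 2023). 5 January 2024 is not.
- Row 3: April contains the window end, so an April date is truly ambiguous and the default is reasonable. Nothing is misflagged before Day 211.

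**Step 4: how much of the gap is decisive.** Share = (post-window days whose calendar month, or year, starts after the window end) ÷ (all post-window days), over the 365 assumed first-dose dates.

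| Follow-up to | Post-window days | In a month wholly after | In a year wholly after | First-dose dates with at least one such day (month / year) |
|---|---|---|---|---|
| Day 211 | 365 × 26 = 9,490 | 4,212 (44.4%) | 351 (3.7%) | 312 / 26 |
| Day 214 | 365 × 29 = 10,585 | 5,219 (49.3%) | 435 (4.1%) | 347 / 29 |
| Day 295 | 365 × 110 = 40,150 | 34,777 (86.6%) | 6,105 (15.2%) | 365 / 110 |

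To Day 211 that is about 0.444 × 26 = 11.5 days per participant if the month is known and about 0.037 × 26 = 1 day if only the year is. Stopping after an assumed last dose on Day 29 gives nearly the same result (44.4% and 3.7%; 311 and 26 dates). In every counted case the rule as written gave treatment-emergent for the partial date and not treatment-emergent for the full date.

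**Step 5: with an upper check added.** If the earliest date compatible with the known year or month is later than last dose + 100 days, the AE is not treatment-emergent. Partial and full dates then agree for the row 1 and row 2 events.

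**The case against.** The strongest reply is that little depends on this. Only 2 participants were enrolled at termination (SAP 1.2), data are only listed (SAP 1), and descriptive summaries are dropped (SAP 4.5). All AEs appear in the listing, so none is lost, and the error runs towards inclusion. It needs a partial date, a late onset, and a month or year wholly past the window. Contacts are 28 days apart from Day 99 to Day 211, and the documents show no such event. All of that stands, and it sets the severity.

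It is also fair to say that the primary endpoint runs through Day 211, so flagging an AE between Day 186 and Day 211 does not conflict with the endpoint's own period. The tension there comes from the 100-day limit. If the window ran to the last follow-up visit, hardly any routinely collected AE could fall after it and the inconsistency would practically disappear. A reader might infer that the fault persists whatever window end is chosen; the collection period in Protocol 8.3.1 does not support that. But the SAP does set 100 days, and under that limit the two branches disagree.

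The convention of defaulting to treatment-emergent is not an answer. It covers ambiguous dates, and these are not ambiguous.

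**Conclusion.** The rule as written gives the wrong flag for a partially dated AE whose known month or year lies wholly after last dose + 100 days, and this can happen within planned follow-up. The size is about 44% of the 26 nominal post-window days when the month is known and about 4% when only the year is, with more under complement extensions. These are shares of days, not error rates. They rest on the assumed 2023 first-dose dates and a last dose on Day 85; for some start dates nothing before Day 211 is affected.

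Two stronger readings are tempting and not supported.

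- A reader might take all post-window time as misflagged: 26/210 = 12%, (26 + 84)/(210 + 84) = 37% with one extension, or 26/126 = 21% after a single dose. Many partial dates in that time contain the window end and are properly left as treatment-emergent. The 84 added days also lie beyond the Day 211 endpoint period.
- A reader might conclude that the primary safety result is biased. This SAP produces no TEAE count or rate and no inference. What can change is an individual listing flag and the related and Grade 3 defaults that follow from it.

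Severity: minor.

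**What to change.** In SAP 6.1:

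1. State that a partially dated AE is treatment-emergent unless the known parts of its start date, or its stop date, place it entirely before the first dose, or the known parts of its start date place it entirely after the window end used for complete dates. Ambiguous and completely missing start dates stay treatment-emergent.
2. Replace the single residual class with two: pretreatment (onset before the first dose) and post-treatment (onset after the window end), for complete and partial dates alike. Without this, the first change would move a late event from treatment-emergent to pretreatment, which is also wrong.

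The cost is two sentences and one extra comparison in the derivation. One consequence to accept knowingly is that a reclassified AE no longer receives the related and Grade 3 defaults, which apply only to treatment-emergent events.

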10.3.3. Recording and Follow-up of AE and/or SAE

Recording of AE and/or SAE

- When an AE/SAE occurs, it is the responsibility of the Investigator to review all documentation (eg, hospital progress notes, laboratory reports, and diagnostics reports) related to the event.
- The Investigator will then record all relevant AE/SAE information in the eCRF.
- It is not acceptable for the Investigator to send photocopies of the participant's medical records to Alexion in lieu of completion of the Alexion AE/SAE eCRF page.
- There may be instances when copies of medical records for certain cases are requested by Alexion. In this case, all participant identifiers, with the exception of the participant number, will be redacted on the copies of the medical records before submission to Alexion.
- The Investigator will attempt to establish a diagnosis of the event based on signs, symptoms, and/or other clinical information. Whenever possible, the diagnosis (not the individual signs/symptoms) will be documented as the AE/SAE.

Assessment of Intensity

The Investigator will make an assessment of intensity for each AE and SAE reported during the study and assign it to one of the following categories from National Cancer Institute CTCAE v5.0, published 27 Nov 2017:

- Grade 1: Mild (awareness of sign or symptom, but easily tolerated)
- Grade 2: Moderate (discomfort sufficient to cause interference with normal activities)
- Grade 3: Severe (incapacitating, with inability to perform normal activities)
- Grade 4: Life-threatening
- Grade 5: Fatal

An event is defined as "serious" when it meets at least one of the predefined outcomes as described in the definition of an SAE, not when it is rated as severe.

Assessment of Causality

- The Investigator is obligated to assess the relationship between the study intervention and each occurrence of each AE or SAE. An Investigator causality assessment must be provided for all AEs (both nonserious and serious). This assessment must be recorded in the eCRF and on any additional forms, as appropriate. The definitions for the causality assessments are as follows:
 - Not related: There is no reasonable possibility the study intervention caused the AE.
 - The AE has a more likely alternative etiology; it may be due to underlying or concurrent illness, complications, concurrent treatments, or effects of another concurrent drug.
 - The event does not follow a reasonable temporal relationship to administration of the study intervention.

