1. INTRODUCTION

This statistical analysis plan describes the plan for presenting the data for final analysis for Protocol ALXN1820-SCD-201. Due to the early termination of the study, data will only be listed.

Safety, pharmacokinetic (PK), pharmacodynamic (PD), immunogenicity, biomarker, demographics and baseline characteristics, medical history, prior and concomitant medications and efficacy data are included. Standard data presentation instructions and listing specifications are contained in the Data Presentation Plan in a separate document.

Changes to the protocol-planned analyses are described in Section 4.5.

Due to the early termination of the study, Cohort 3 will not be initiated, the planned interim analysis will not be conducted, and the output of all participants will be listed without inclusion of tables and figures.

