4.2.1. Analysis of AEs

All the AEs will be listed for each participant.

The adverse event will be presented using primary Medical Dictionary for Regulatory Activities (MedDRA) System Organ Classes (SOCs) and Preferred Terms (PTs) according to the version of the MedDRA coding in effect dictionary at the time of database lock. The SOCs will be presented in alphabetical order, and the PTs will be presented in descending order of frequency overall within each SOC.

Treatment-emergent adverse events (TEAEs) (refer to Section 6.1 for the definition of TEAE) will be indicated. The following information of AEs will also be listed:

- Relationship as assessed by the investigator
- Severity by severity grades according to the National Cancer Institute (NCI) Common Terminology Criteria for Adverse Events (CTCAE, v5.0) (Grade 1, Grade 2, Grade 3, Grade 4, Grade 5)
- Seriousness criteria
- VOC exacerbated
- Leading to discontinuation from study intervention

- Leading to study withdrawal
- Leading to death
- Injection site reaction (ISR) according to the Investigator.

Clinically significant ISR will be reported as AE and will be indicated on the AE listing.

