4.5. Changes to Protocol-Planned Analyses

Due to the early termination of the study and limited enrolled participants, data will only be listed. Applicable changes from Protocol Amendment 1.0 are as follows:

- The interim analyses have been removed

- The Cohort 3 will not be initiated and have been removed
- Analysis sets have been removed except for Enrolled Set, all analyses will be based on the Enrolled Set
- Analyses of PK parameters have been removed
- Summary descriptive statistics will not be provided
- Outlier analyses of ECG have been removed
- Inflammatory biomarkers and cell adhesion biomarkers have been removed from the analysis of VOC-related biomarkers
- Visit windows have been removed

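### SAP 6.1 still imputes missing severity and relationship for TEAEs in a listings-only report, with no requirement to flag the derived values

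*SAP*

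**What the plan says.** SAP 6.1 (Technical Specifications for Derived Variables, Adverse Events) has two rules for incomplete TEAE records. If the relationship is blank, "then the relationship will be counted as related to study intervention for the listing tables". For severity, "Missing severity for TEAEs will be counted as Grade 3".

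The report these rules feed is described in SAP 1: "Due to the early termination of the study, data will only be listed". The same section rules out tables and figures, and SAP 4.5 adds: "Summary descriptive statistics will not be provided".

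SAP 4.2.1 sets out the content of the AE listing. Its items include "Relationship as assessed by the investigator", the severity grade, the seriousness criteria and "Leading to death".

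Protocol 10.3.3 gives the severity scale, with "Grade 4: Life-threatening" and Grade 5 for a fatal event. It also makes the assessment mandatory: "The Investigator will make an assessment of intensity for each AE and SAE reported during the study". Causality is required for every AE in the same section.

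**The concern.** Setting a missing grade or relationship to an unfavourable value is a familiar convention for summary tables. It stops incomplete records from lowering the count of severe or related events. Once the summaries are dropped, that purpose goes, and the rule can act only on individual rows of a listing.

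This matters because a listing is normally read as a record of what was collected. With 2 participants enrolled at termination (SAP 1.2), readers will look at single rows. If a derived value were printed without a mark, a related, Grade 3 event that the investigator recorded would look the same as one where both fields were blank. The fixed Grade 3 also sits below the top of the scale, so for the most serious events the imputation would understate severity.

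**Working it through.** There is no figure in the plan to reproduce; the point rests on applying the text as written.

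**1. Where can the imputed values appear?** The relationship rule names the listings. The severity rule does not, but SAP 1 and 4.5 leave no other output. The one trace of counting in SAP 4.2.1 is the ordering of preferred terms by frequency, and that uses neither grade nor relationship. So no count uses the imputed values.

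**2. What does the severity rule do to each possible record?**

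| Grade recorded for a TEAE | Outcome | Grade under SAP 6.1 | Grade on the protocol scale |
|---|---|---|---|
| 1 to 5 | any | unchanged | as recorded |
| blank | neither life-threatening nor fatal | 3 | unknown |
| blank | life-threatening | 3 | 4 |
| blank | fatal | 3 | 5 |

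In the last row the listing would show Grade 3 beside a positive entry for death, so the row would disagree with itself. In the row above it, Grade 3 could stand beside a life-threatening entry under the seriousness criteria.

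**3. Relationship.** SAP 4.2.1 promises the investigator's judgement. Where none was recorded, a derived value of related is not that judgement. SAP 6.1 does not say whether the derived value goes in the same column, in a second column, or with a mark.

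**4. Consistency within the listing.** SAP 4.2.1 lists all AEs, but SAP 6.1 imputes for TEAEs only. Two records with the same blank field would therefore be handled differently, depending on treatment-emergent status.

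**5. Consistency within the SAP.** For PK concentrations, SAP 4.3.1 has missing results labelled as missing in the listing. The AE section has no such provision.

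**6. How often could this arise?** The documents give no rate of missing grades or relationships and report no such case. Protocol 10.3.3 requires both assessments for every AE, and causality before an SAE is first transmitted. With 2 participants, few if any blanks should remain at database lock.

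**The case against.** The strongest reply is that this is ordinary SAP structure. SAP 4.2.1 names the variable and SAP 6.1 supplies a fallback when it is blank. A recorded assessment is never changed, and counting a blank as related cannot understate drug relationship. The listing layouts are in a separate Data Presentation Plan (SAP 1), which may show the recorded field, the derived field or a flag. The protocol makes blanks unlikely in any case.

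Most of this stands, and it rules out several stronger readings that a reader might infer:

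- *That collected data are overwritten.* SAP 6.1 speaks of counting missing values in a certain way, under derived variables. It does not say that the collected field is replaced.
- *That imputed values will be indistinguishable from recorded ones.* The SAP does not require a flag, but the Data Presentation Plan, which is not available here, could provide one.
- *That a death could be concealed.* The death item and the seriousness criteria are in the same listing. The result would be a visible inconsistency.
- *That the AE listing is the whole primary-endpoint output.* SAP 4.2 also includes laboratory, vital-sign, physical-examination and ECG data, each with its own listing.

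The reply leaves two things unanswered. It gives no purpose for the imputation in a report without summaries, and it does not explain why Grade 3 should apply to an event recorded as fatal or life-threatening.

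**Conclusion.** The point holds as a low-impact correction. Followed literally, SAP 6.1 produces derived entries in participant-level AE listings for no analytical gain. For a fatal or life-threatening TEAE with a blank grade, it produces an entry two grades (5 − 3) or one grade (4 − 3) below the protocol scale. No inferential result or decision rule in the SAP depends on these values.

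The conclusion assumes that the severity rule, like the relationship rule, is meant for the listings, since there is no other output. It also assumes that no flagging is specified elsewhere. If the Data Presentation Plan already shows recorded and derived values side by side, the flagging concern falls away. The missing exception for fatal and life-threatening events would remain.

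**What to change.** In SAP 6.1, replace the two imputation sentences with a statement that severity and relationship are listed as recorded and that blanks are labelled as missing, in line with SAP 4.3.1.

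If the sponsor prefers to keep a derived value, the SAP should place it in a separate, flagged column beside the recorded one. It should also state that Grade 3 is not derived for an event recorded as fatal or life-threatening.

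The cost is a wording change in the SAP and a check that the Data Presentation Plan agrees. The first option needs less programming than the current rule, and no further data are needed.
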